10.2 Monitoring and reporting guidelines

Investigators will conduct continuous review of data and patient safety at weekly meetings where the results of each patient's treatment are discussed and documented in the minutes. The discussion will include the number of patients, significant toxicities as described in the protocol, doses adjustments, and observed responses. All grade 3-5 AE's and SAE's will be entered in the HDFCCC Clinical Trials Management System. All institutional Phase 2 studies are designated with a moderate risk assessment; therefore, the data is monitored every six months, with twenty percent of the subjects monitored (or at least three subjects if the calculated value is less than three).

10.3 Regulatory considerations

This study will be reviewed by the UCSF-HDFCCC Protocol Review Committee, in addition to the UCSF IRB (the Committee on Human Research, or CHR). Participating sites will submit this study to the relevant local IRB for review.

10.4 Independent ethics committees / Institutional Review Board

This protocol and the informed consent will be approved by the IRB at all sites. The Principal Investigator at each site is responsible for keeping the IRB advised of the progress of the study and of any changes made in the protocol prior to implementation. The Principal Investigator will also keep the IRB informed of any significant adverse reactions (see section 11.0), and any protocol exceptions or deviations. Records of all study review and approval documents must be kept on file by the Principal Investigator and are subject to FDA inspection during or after completion of the study. The IRB at all sites will receive notification of the termination of the study.

11.0 Adverse Events

11.1 Grading adverse events and serious adverse events

This study will use the NCI Common Terminology Criteria for Adverse Events version 4.0 (CTCAE v 4.0) found at the following website: <http://evs.nci.nih.gov/ftp1/CTCAE/About.html> for grading the severity of adverse events. The investigator is responsible for making an assessment of whether or not it is reasonable to suspect a causal relationship between the adverse event and the study treatment.

11.2 Adverse Event Review and Monitoring

The investigator or qualified designee will assess each subject to evaluate for potential new or worsening AEs as per the study schedule, and more frequently if clinically indicated. Adverse experiences will be graded and recorded throughout the study and during the follow-

up period. Toxicities will be characterized in terms regarding seriousness, causality, toxicity grading, and action taken with regard to trial treatment.

11.3 Definition of Adverse Event

An adverse event (also known as an adverse experience) is defined as any untoward medical occurrence associated with the use of the study intervention in humans, whether or not considered drug related. More specifically, an adverse event can be any unfavorable and unintended sign (e.g., an abnormal laboratory finding), symptom, or disease temporally associated with the study intervention, without any judgment about causality. An adverse event can arise from any use of the study intervention (e.g., off-label use, use in combination with another treatment) and from any route of administration, formulation, or dose, including an overdose.

11.4 Adverse reaction

An adverse reaction is defined as any adverse event caused by the study intervention. Adverse reactions are a subset of all suspected adverse reactions for which there is reason to conclude that the study intervention caused the event.

11.6 Suspected

A suspected adverse reaction is defined as any adverse event for which there is a reasonable possibility that the study intervention caused the adverse event. For the purposes of safety reporting, “reasonable possibility” indicates that there is evidence to suggest a causal relationship between the study intervention and the adverse event. A suspected adverse reaction implies a lesser degree of certainty about causality than an adverse reaction.

11.7 Unexpected

An adverse event or suspected adverse reaction is considered unexpected if it is not listed in the investigator brochure or package insert(s), or is not listed at the specificity or severity that has been observed, or, if an investigator brochure is not required or available, is not consistent with the risk information described in the general investigational plan or elsewhere in the current application.

“Unexpected,” as used in this definition, also refers to adverse events or suspected adverse reactions that are mentioned in the investigator brochure as occurring with a class of drugs or as anticipated from the pharmacological properties of the drug, but are not specifically mentioned as occurring with the particular drug or study intervention under investigation.

11.8 Life-threatening

An adverse event or suspected adverse reaction is considered life-threatening if, in the view of the study PI, its occurrence places the patient or subject at immediate risk of death. It does not include an adverse event or suspected adverse reaction that, had it occurred in a more severe form, might have caused death.

11.9 Evaluation of an Adverse Event

All grade 3 and above adverse events will be entered into OnCore®, whether or not the event is believed to be associated with use of the study drug.

The Investigator will assign attribution of the possible association of the event with use of the investigational drug, and this information will be entered into OnCore® using the classification system listed below:

Relationship	Attribution	Description
Unrelated to investigational drug/intervention	Unrelated	The AE is clearly NOT related to the intervention
	Unlikely	The AE is doubtfully related to the intervention
Related to investigational drug/intervention	Possible	The AE may be related to the intervention
	Probable	The AE is likely related to the intervention
	Definite	The AE is clearly related to the intervention

Signs or symptoms reported as adverse events will be graded and recorded by the Investigator according to the CTCAE. When specific adverse events are not listed in the CTCAE they will be graded by the Investigator as none, mild, moderate or severe according to the following grades and definitions:

- Grade 0 No AE (or within normal limits)
- Grade 1 Mild; asymptomatic or mild symptoms; clinical or diagnostic observations only; intervention not indicated
- Grade 2 Moderate; minimal, local, or noninvasive intervention (e.g., packing, cautery) indicated; limiting age-appropriate instrumental activities of daily living (ADL)
- Grade 3: Severe or medically significant but not immediately life-threatening; hospitalization or prolongation of hospitalization indicated; disabling; limiting self-care ADL
- Grade 4: Life-threatening consequences; urgent intervention indicated
- Grade 5: Death related to AE

11.10 NCI Common Terminology for Adverse Events (CTCAE)

An investigator who is a qualified physician will evaluate all adverse events according to the NCI Common Terminology for Adverse Events (CTCAE), version 4.0. Any adverse event which changes CTCAE grade over the course of a given episode will have each change of grade recorded as per study requirements.

All adverse events regardless of CTCAE grade must also be evaluated for seriousness.

11.11 Follow-up of Adverse Events

All adverse events will be followed with appropriate medical management until resolved. Patients removed from study for unacceptable adverse events will be followed for 90 days or until resolution or stabilization of the adverse event. For selected adverse events for which administration of the investigational treatment was stopped, a re-challenge of the subject with the investigational treatment may be conducted if considered both safe and ethical by the

Investigator.

11.12 Adverse Events Reporting

The Study Chair will assess all adverse events and determine reportability requirements to the UCSF Data and Safety Monitoring Committee (DSMC) and UCSF's Institutional Review Board, and the Committee on Human Research (CHR). Adverse events will be reported to the DSMC via OnCore.[®]

All adverse events entered into OnCore[®] will be reviewed by the Helen Diller Family Comprehensive Cancer Center Site Committee on a monthly basis. The Site Committee will review and discuss monthly the selected toxicity, the toxicity grade, and the attribution of relationship of the adverse event to the administration of the study treatment.

All grade(s) 3-5 adverse events entered into OnCore[®] will be reviewed on a monthly basis at the Site Committee meetings. The Site Committee will review and discuss the selected toxicity, the toxicity grade, and the attribution of relationship of the adverse event to the administration of the study treatment.

In addition, all suspected adverse reactions considered "serious" entered into OnCore[®], will be reviewed and monitored by the Data and Safety Monitoring Committee on an ongoing basis and discussed at DSMC meetings, which take place every six weeks.

Adverse event reporting will continue until 24 months post-transplant, or until 90 days after the patient stops trial participation, if applicable.

11.14 Expedited Reporting

The following adverse events, when they occur in patients undergoing withdrawal of immunosuppression or DLI, must be reported to the Study Chair within 10 days of occurrence:

- Any evidence of acute or chronic GVHD toxicities of any organ of Grade III or higher (using CTCAE v. 4.0)
- Any change in GVHD prophylaxis or conditioning regimen outside of the planned GVHD prophylaxis taper.
- Any invasive fungal infection or disease caused by viral infections in patients treated with immunosuppression for GVHD that developed following study intervention
- Inpatient hospitalization or prolongation of existing hospitalization
- Relapse of leukemia/malignancy.

Reporting to the Data and Safety Monitoring Committee

If a death occurs during the treatment phase of the study or within 30 days after the last administration of the study treatment and it is determined to be related either to the study drug(s) or to a study procedure, the Investigator or his/her designee must notify Study Chair within one business day of knowledge of the event, who must then notify the DSMC Chair (or qualified alternate) within 1 business day. The contact may be by phone or e-mail.

Reporting Committee on Human Research (Institutional Review Board)

The Study Chair must report events meeting the UCSF CHR definition of "Unanticipated Problem" (UP) within 10 business days of his/her awareness of the event. Participating site Principal Investigators must report events to their IRB as per institutional guidelines.

Reporting Requirements for participating sites:

Any adverse event meeting SAE criteria must be reported to UCSF within 24 hours of the site learning about the event.

- SAEs must be reported to UCSF PI via the SAE Case Report Form:

- SAEs and Safety Reports will be submitted to IRBs as per local requirements.

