6.0 Toxicity Management and Dose Modifications

6.1 DLI Toxicity: GVHD

- DLI will be GCSF-mobilized unless otherwise specified; DLI dose modifications may be made on a case-by-case basis. See Appendix 3 for additional details regarding toxicity management.
- As soon as GVHD is suspected, all further DLI or withdrawal of immunosuppression should be stopped and the patient monitored, regardless of chimerism or MRD status.
- Azacitidine may continue at the discretion of the treating physician for grade I-II acute GVHD (aGVHD) or mild chronic GVHD (cGVHD).
- If aGVHD or cGVHD is confirmed, the patient should initiate therapy as per institutional standard of care.
- All instances of aGVHD or cGVHD in patients in the intervention group should be reported to the study chair within 10 days of learning about them, and grade III-IV aGVHD and severe cGVHD should be reported within 24 hours of learning about them (see Adverse Events Section 11.0).
- At each instance of grade III-IV aGVHD or cGVHD reported in the study, subgroup analysis will be performed in the high-risk group in order to monitor safety of DLI, as outlined in section 8.7.

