8.7.3 Stopping rules for interim toxicity and relapse futility

- Study data will be analyzed for relapse rates within 3 months for efficacy assessment. Such early futility assessment will be done when the first 14 patients have completed the 3-month follow-up in the study. If there are 9 or more relapses out of 14 patients during the futility assessment, enrollment will be stopped due to futility. Otherwise an additional 54 patients will be accrued for a total of 67 patients in the study. By the end of the study, if there are 32 or more relapses observed, further investigation will not proceed. In this study the rate of relapse in pediatric acute leukemia post-transplant is assumed to be 40% (as shown in our pilot study), azacitidine +/- DLI would reduce the 2-year relapse rate by approximately 40% to a rate of 25% and that the toxicity rate in pediatric acute leukemia post-transplant under azacitidine +/- DLI would be 20%. The stopping rules for toxicity and relapse rate under sequential design of multiple endpoints are shown below:
- For patients receiving DLI, a subset analysis of incidence of Grade III-IV aGVHD and mortality secondary to GVHD will be performed when a new patient is diagnosed with Grade III-IV GVHD or chronic GVHD.
 - Reported rates of grade III-IV acute GVHD following DLI range from 20-35%; GVHD-related mortality ranges from 5-15%.
 - If rates of Grade III-IV aGVHD or GVHD-related mortality in this study exceed published rates, enrollment and further DLI administration will be suspended while further safety analysis is performed.

Patients on Study	<14	15-21	22-28	29-35	36-42	43-49	50-56	57-63
Number of patients with SAE (Toxicity)	>8	≥10	≥13	≥16	≥18	≥21	≥23	≥26
Number of patients with relapse in 3 months	>9	≥13	≥16	≥19	≥23	≥26	≥29	≥32

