11.16 SAE Reports Associated with Study Stopping Rules

The following SAEs have a potential to trigger study stopping rules (see Section 8.7) and must be reported to the Study Chair within 24 hours:

- 11.16.1 aGVHD of grade IV
- 11.16.2 Severe cGVHD
- 11.16.3 Any organ toxicity of grade IV (using CTC Common Toxicity criteria version v4.0) that is judged to be related to withdrawal of immunosuppression, azacitidine, or DLI.
- 11.16.4 Any death judged to be related to fast immunosuppression withdrawal, azacitidine, or DLI.
- 11.16.5 Note: investigators must report any aGVHD grade IV, severe cGVHD, any organ grade IV toxicity or any death in patients undergoing immunosuppression withdrawal to the Study Chair within 24 hours. Judgment about contribution of withdrawal of immunosuppression to the reported severe event will be made by DSMC within 10 days.
- 11.16.6 Phone or fax reports of SAE's due within 24 hours to:
[REDACTED]

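### Grade III acute GVHD can trigger the DLI safety review in 8.7.3, but 6.1 wants it reported in 24 hours, 11.14 allows 10 days, and the 24-hour list in 11.16 omits it

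*Combined protocol and SAP*

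**What the plan says.** Four sections of the combined protocol and SAP bear on this.

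- **8.7.3 (stopping rules).** For patients receiving DLI, a subset analysis of grade III-IV acute GVHD and GVHD mortality "will be performed when a new patient is diagnosed with Grade III-IV GVHD or chronic GVHD". If either rate exceeds published rates (quoted there as 20-35% for grade III-IV acute GVHD and 5-15% for GVHD-related mortality), "enrollment and further DLI administration will be suspended while further safety analysis is performed".
- **6.1 (DLI toxicity).** All acute or chronic GVHD goes to the study chair within 10 days, but "grade III-IV aGVHD and severe cGVHD should be reported within 24 hours of learning about them". The same section ties the subgroup analysis to each grade III-IV case that is reported, and refers the reader to section 11.
- **11.14 (expedited reporting).** For patients undergoing withdrawal of immunosuppression or DLI, the listed events "must be reported to the Study Chair within 10 days of occurrence". The first is "Any evidence of acute or chronic GVHD toxicities of any organ of Grade III or higher (using CTCAE v. 4.0"). Inpatient hospitalization is on the same list. Lower in the section, for participating sites: "Any adverse event meeting SAE criteria must be reported to UCSF within 24 hours of the site learning about the event".
- **11.16 (SAE reports tied to stopping rules).** This section presents itself as the list of SAEs that could trigger the section 8.7 rules and are due in 24 hours. Its only acute GVHD entry is "11.16.1 aGVHD of grade IV". Note 11.16.5 repeats grade IV.

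**The concern.** The DLI review in 8.7.3 can act only on cases that have reached the study chair. Grade III acute GVHD counts toward its trigger, yet the section that sites are sent to for reporting gives the longer limit and leaves grade III off the list of stopping-rule events. Both 6.1 and 8.7.1 direct the reader to section 11. In addition, 6.1 is phrased as *should* and 11.14 as *must*, so a site could reasonably treat section 11 as governing.

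What is at stake is the timeliness of a rule meant to protect other children who are due for DLI. While a grade III case is unreported, the observed rate compared with the published range is too low, and enrollment and DLI continue. Grade III is not peripheral elsewhere in the plan: it is in hypothesis 2.3.2, the primary safety endpoint (8.3.2) and the planned analysis (8.6.2).

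**Working it through.** The plan gives no figure to reproduce. The check is a comparison of the text plus one subtraction.

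**Step 1. Set the sections side by side.**

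| Section | Event | Limit | Clock starts |
|---|---|---|---|
| 6.1 | Grade III-IV acute GVHD; severe chronic GVHD | 24 hours | Learning of the event |
| 6.1 | Other acute or chronic GVHD | 10 days | Learning of the event |
| 11.14 | GVHD toxicities, grade III or higher (CTCAE) | 10 days | Occurrence |
| 11.14, 8.7.2 | Any event meeting SAE criteria | 24 hours | Learning of the event |
| 11.16 | Grade IV acute GVHD; severe chronic GVHD | 24 hours | Not stated |
| 8.7.3 | Grade III-IV GVHD or chronic GVHD | Starts the DLI review | Diagnosis |

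**Step 2. Find which cases fall through.** Grade IV acute GVHD and severe chronic GVHD are due in 24 hours under both 6.1 and 11.16, although 11.14 also puts them on its 10-day list. Grade III acute GVHD is due in 24 hours under 6.1 only. If it meets the seriousness criteria in section 11, for example through hospitalization, the general SAE rule also gives 24 hours. Those criteria do not name grade III acute GVHD, so a case managed without admission need not qualify. The exposed group is grade III acute GVHD not classed as an SAE. The documents do not say how many cases that would be.

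**Step 3. Size the gap.** Let d be the days from occurrence until the site learns of the case, and treat the 10 days as calendar days.

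- Deadline under 6.1, counted from occurrence: d + 1 days.
- Deadline under 11.14, counted from occurrence: 10 days.
- Added delay: 10 − (d + 1) = 9 − d days.

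With d = 0 the gap is 9 days. With d = 3 it is 6 days. With d = 9 it is zero. Nine days is therefore a maximum.

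**Step 4. Put 9 days in context.** Planned accrual is 67 patients over 2 years (8.5.1): 67/730 = 0.092 per day, and 0.092 × 9 = 0.8 further enrollments. Against the 6-week cycle in 3.1.3, 9/42 = 21% of a cycle.

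**The case against.** The strongest case on the other side has five parts.

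1. **A site can satisfy every section by using the shortest limit.** True, but only if it notices that 6.1 is stricter than the reporting section to which 6.1 itself refers.
2. **The 11.14 bullet may not mean overall acute GVHD grade.** It uses CTCAE organ grading and may be two items run together: any GVHD, and any grade III organ toxicity. Read so, it echoes the 10-day tier in 6.1. This ambiguity stands, but on either reading grade III acute GVHD can fall under 10 days.
3. **Grade IV in 11.16 may be deliberate.** The protocol summary defines success by grade IV GVHD, and the SAE boundaries in 8.7.2 assume an acceptable rate of 20%. Adding grade III to 11.16 without qualification could change what counts toward those boundaries. This stands and shapes the fix. It does not explain why a list tied to section 8.7 as a whole omits a trigger in 8.7.3.
4. **Other safeguards exist.** Section 6.1 stops DLI for the affected patient once GVHD is suspected, and 10.2 describes weekly investigator meetings on each patient's results. These limit the harm but do not settle the reporting deadline.
5. **One report does not suspend anything.** It starts an analysis, and suspension follows only if rates exceed published ones. This stands.

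Some stronger readings are tempting but not supported. A reader might infer that each late case leads to further infusions that the rule would have prevented; the documents do not give the number of patients on DLI, and most cases would not cross the threshold. A reader might infer that 11.14 plainly contradicts itself on hospitalization; the 10 days there could be the written step that 8.7.2 adds to its 24-hour notice, though 11.14 does not say so. A reader might infer that all chronic GVHD should be due in 24 hours because it triggers 8.7.3; 6.1 expressly leaves non-severe chronic GVHD at 10 days. Nothing in the documents shows that the delay would differ between sites.

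**Conclusion.** The sections conflict on the reporting of grade III acute GVHD, and the conflict touches an operative safety rule. For a grade III case that is not an SAE, a site following section 11 exactly could report up to about 9 days later than 6.1 intends, and the study-level DLI review would start correspondingly late. That figure assumes that the site learns of the case as it occurs; it shrinks day for day if the site learns later. The practical effect is modest, because the patient's own DLI has already stopped and the delay alters a decision only when the unreported case would have taken the rate past the published range. The 8.7.3 rule is weakened in timing, not disabled. The correction is cheap and worth making.

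**What to change.** Reconcile 6.1, 8.7.3, 11.14 and 11.16 on grade, clock and limit, so that section 11 carries the 24-hour limit already in 6.1.

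- **11.16 and note 11.16.5:** add grade III acute GVHD as a reportable trigger for the 8.7.3 DLI review. State that this does not alter which events count toward the SAE boundaries in 8.7.2 and 8.7.3.
- **11.14:** take grade III-IV acute GVHD and severe chronic GVHD off the 10-day list, and start the clock when the site learns of the event, as in 6.1.
- **11.14, hospitalization:** state that an admission meeting SAE criteria is due in 24 hours and that 10 days applies only to the written follow-up described in 8.7.2.
- **Non-severe chronic GVHD:** leave at the 10 days in 6.1.

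The cost is a wording amendment and a few more 24-hour reports, which 6.1 already asks for. With the statement on what counts, the SAE stopping boundaries stay as they are.

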11.15 Review of adverse event rates

If the study has an increase of unexpected or expected Severe Adverse Events above the rate reported in this protocol, the increased rate of AEs will be reported to the DSMC at the time of identification. The DSMC Chair and Study Chair will discuss the findings and proceed with a written course of action. If at any time the Study Chair stops enrollment or stops the study due to safety issues the DSMC Chair must be notified within 24 business hours via e-mail. The DSMC must receive a formal letter within 10 business days and the IRB must be notified.

If any of the above action occurs in multiple-institutional clinical trial, the Study Coordinator will insure that all participating sites are notified.

